#### **4.3 Inclusion of Women and Minorities**

Both men and women (as applicable) and members of all races and ethnic groups are eligible for this trial.

Men develop breast cancer at 1%, thus, the study population will be primarily female. These estimates are based on the following: the population pool from which patients will be drawn in Washington state is 83.8% Caucasian, 7.0% Asian American, 3.9% African American, 1.8% American Indian or Alaska Native and 0.5% Native Hawaiian or Other Pacific Islander. The population pool from which patients will be drawn at the University of Wisconsin is 93% Caucasian, 2% Asian American, 3% African American, 1% American Indian or Alaska Native, 0% Native Hawaiian or other Pacific Islander and 1% other/unknown. This would give a total average between Wisconsin and Washington of 88.4% Caucasian, 4.5% Asian American, 3.45% African American, 1.4% American Indian or Alaska Native, and 0.25% other/unknown.

#### **5. AGENT ADMINISTRATION**

Vaccines will be administered on an outpatient basis either at the University of Washington Clinical Research Center (UW CRC) or the University of Wisconsin Clinical Research Unit (UWI CRU).

Reported adverse events (AEs) and potential risks are described in Section 6.2.

##### **5.1 Dose Regimen and Dose Groups**

There will be three treatment groups for this trial:

- Arm 1: WOKVAC (150 mcg) with Sargramostim (rhuGM-CSF) (100 mcg); administered as 1 i.d. injection every month for 3 total doses.
- Arm 2: WOKVAC (300 mcg) with Sargramostim (rhuGM-CSF) (100 mcg); administered as 2 i.d. injections every month for 3 total doses.
- Arm 3: WOKVAC (600 mcg) with Sargramostim (rhuGM-CSF) (100 mcg); administered as 3 i.d. injections every month for 3 total doses.

##### **5.2 WOKVAC Administration**

Standard precautions should be taken when handling the vaccine/GM-CSF. Gloves and lab coats should be worn per the standard of the clinic administering the vaccine. Caution should be taken when handling the vaccine that is prepared by the pharmacy in syringes. Sharps containers should be readily available. The vaccine is administered intradermal (i.d.). It should be injected slowly to avoid any vaccine leaking

out from under the skin. Standard reporting procedures should be implemented as needed per the standard of the clinic.

Patients with axillary lymph node dissection (ALND) will have vaccine administered to the contralateral arm. Patients with bilateral ALND will have vaccine administered in the thigh. As much as possible each vaccine dose will be given within the same draining lymph node site.

Study clinicians will administer vaccines using professional standards of medication administration that include:

- Right patient, right vaccine, right dose, right route, right site.
- Personnel who will administer vaccines will have received training and education on vaccine administration and disposal before providing vaccines to patients.

One dose of the vaccine may be given in several injections in the same general area once a month for three months. Patients will be monitored for a minimum of 60 minutes post vaccine administration. Acute hypersensitivity and/or anaphylactic reactions are very rare with reported rates ranging from 0.22 - .065 per 100,000 doses of vaccinations.  Additionally, anaphylactic reactions to vaccines should they occur, usually appear within 5 to 60 minutes.

### **5.3 Run-in Procedures**

There is no run-in phase for this study.

### **5.4 Contraindications**

Patients should not be pregnant or become pregnant through the 6 month follow-up visit. Patients should not concurrently enroll in any other treatment study.

### **5.5 Concomitant Medications**

Throughout the duration of the study patients should not be on cytotoxic chemotherapy, systemic steroids, monoclonal antibody, and/or other biologic therapy. Exceptions are bisphosphonates, denosumab, and endocrine-based therapy. All medications (prescription and over-the-counter), vitamin and mineral supplements, and/or herbs taken by the patient will be documented in their study chart through the 6 month follow-up visit and may include: 1) start and stop date, dose and route of administration, and indication. Medications taken for a procedure (*e.g.*, biopsy) should also be included.

### **5.6 Dose Modification**

There are no dose modifications as part of this protocol. There may be allowances for the timing of the administration of vaccine to accommodate for special circumstances including repeated blood glucose testing. Subsequent vaccinations will be scheduled 28 (+ 7) days from when the previous vaccine was actually administered, not when it should have been administered.

### **5.7 Adherence/Compliance**

- 5.7.1. All patients who receive any vaccinations will be evaluated for primary endpoint of safety.
- 5.7.2. Patients who have baseline and at least one post vaccine research blood sample will be evaluated for immune response.
- 5.7.3. Compliance will be assessed by tracking visit dates and completion of protocol procedures.

## **6. PHARMACEUTICAL INFORMATION**

## 6.1 WOKVAC

**(IND#16870), IND Sponsor: [name], MD, University of Washington, Seattle, WA**

### WOKVAC Vaccine

The plasmid we will use clinically is pUMVC3-IGFBP2-HER2-IGF1R(WOKVAC) and contains a total of 5947 base pairs. A DNA insert encoding the N-terminal 163 amino acids of IGFBP2, HER2 amino acids 686-994/1036-1051/1156-1197 and IGF1R amino acids 1196-1261/1323-1360 has been inserted between the Kpn1 (at base 1125) and Not1 restriction sites.

The WOKVAC vaccine is supplied in single-use vials as a sterile, frozen solution. Each single use vial has a final concentration of 1 mg of DNA/ 1mL tromethamine/EDTA (TE). Each WOKVAC vaccine will carry a label bearing the drug identification and conditions for storage.

### GM-CSF

Reconstituted recombinant human GM-CSF (rhuGM-CSF, Sargramostim) as a 100 mcg dose will be used as adjuvant admixed with WOKVAC plasmid based vaccine.

RhuGM-CSF is a sterile, white, preservative-free lyophilized powder in 250 mcg vials.

## 6.2 Reported Adverse Events and Potential Risks

This is the first time that this investigational vaccine has been used in humans. Although there were no serious side effects seen in mice given the vaccine, it is possible that humans will have a different response than the mice.

### Risk of Study Vaccine

UW has given over 1100 peptide/DNA plasmid vaccine injections in previous studies, and below are some possible risks:

Likely	Less likely	Rare, some may be serious
Pain and discomfort during vaccine administration	Flu-like syndrome	Allergic reaction, including shortness of breath, dizziness, a feeling of fainting, hives, and difficulty breathing caused by swelling of the mouth, face, tongue or throat
Redness and tenderness at injection site (this usually goes away in 1-2 days)	Muscle pain	
Itching at vaccine site	Nausea	
Fatigue	Chills	Severe allergic reaction to the vaccine may require medication, lead to hospitalization, and may result in death
Headache	Diarrhea	
		Hyperglycemia

Risk of Granulocyte-Macrophage Colony Stimulating Factor (rhuGM-CSF, Sargramostim)

GM-CSF is a man-made protein that is almost identical to a protein the body makes, and will be mixed and injected in very small amounts with the vaccine. GM-CSF is also known as an adjuvant. In our previous vaccine studies that used GM-CSF, patients sometimes complained of mild to moderate flu like symptoms (fever, chills, achiness, and fatigue) for 1-2 days after vaccination that may be related to the use of GM-CSF. The possible risks listed below are for a larger dose of GM-CSF than will be given in this study; patients will be getting a fraction of the regular GM-CSF dose.

Likely	Less likely, some may be serious	Rare, some may be serious

Local reactions at the site of the injection
 
Low grade fever (less than 100.5°F)
 
Chills
 
Pain in the bones, muscles, chest, abdomen, or joints
 
Nausea
 
Vomiting
 
Diarrhea
 
Flu-like symptoms including fatigue, weakness, headache
 
Decreased appetite
 
Increased white blood cell count
	
Kidney and liver problems
 
Local reactions at the site of injection
 
Rashes
 
Liver enlargement
 
Low blood pressure
	
Fluid retention (including fluid in lungs or around the heart)
 
Blood clotting, including blood clots in the leg veins that can break loose and go to the lung
 
Increased platelets, low albumin, increase of liver enzymes
 
Rapid or irregular heartbeat or other heart problems
 
Allergic reaction, including shortness of breath, dizziness, a feeling of fainting, hives, and difficulty breathing caused by swelling of the mouth, face, tongue or throat
 
Worsening of pre-existing fluid accumulation in arms and legs, in the lungs and around the heart that may result in breathing problems and heart failure
 
Neurologic syndrome called Guillain-Barré syndrome, where a person's own immune system damages their nerve cells, causing muscle weakness and sometimes paralysis
 
Temporary loss of consciousness

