We have experience immunizing with two of the three components of WOKVAC in our clinical plasmid; HER2 and IGFBP-2. We have completed a 66 patient study of pUMVC3-HER2 ICD. Immunizing advanced stage breast cancer patients against pUMVC3-HER2 ICD did not result in significant toxicity. A total of 990 adverse events (AEs) were recorded. Ninety-nine percent of collected AEs were grades 1 and 2, but only 52% of those recorded were possibly, probably or definitely related to vaccination. The most common AEs were reaction at the injection site, and flu-like syndrome. All reactions at the injection site were attributable to the vaccine; however, only 82% and 78% of the fatigue and flu-like syndrome, respectively, were attributable to the vaccine. pUMVC3-HER2 ICD also did not induce clinically significant autoimmunity. We evaluated for the development of serologic autoimmunity, only four patients exhibited decreased complement C3, 2 patients had a positive antinuclear antibody (ANA) defined by titers of  $\geq 1:160$  by immunofluorescence (IF) and no patient developed clinical evidence of autoimmune disease. Lymphocytes from study patients were evaluated for presence of vector pre- and 1 month post-vaccination. If persistent DNA was detected at 1 month, serial assessment for vector presence was continued at 3, 6, and 12 months after the last vaccine, or until DNA was no longer detected. There was no detection of DNA plasmid in lymphocytes from patients immunized. No significant vaccine induced cardiac toxicity was observed and all cardiac toxicities observed on the study were either Grade 1 or Grade 2. In addition, those patients receiving concurrent trastuzumab during vaccination (n=31) across all arms, the median LVEF pre- and post-vaccination was 61% and 60%, respectively.

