## 7. CLINICAL EVALUATIONS AND PROCEDURES

### 7.1 Schedule of Events

Evaluation/ Procedure	Baseline 	1 st vaccination	2 nd , 3 rd vaccination 	Post-vaccination Follow-up Visits 	Long-term Follow-up 
Informed Consent	X				
Assess Eligibility	X				
Medical History	X				
Baseline Symptom Assessment	X				
Physical Exam 	X		X	X	
Vital Signs/ and Weight	X	X	X	X	
Concomitant Medications	X	X	X	X	
Assign dose arm	X				
Urine Pregnancy Test 	X	X	X		
CBC 	X	X 	X	X	
CMP 	X	X	X	X	
HbA1c	X			X	
GAD65		X		X	
ANA, anti-dsDNA, C3 and TSH		X	X	X	
Research Blood 		X		X	
Tetanus- diphtheria Immunization 		X			
MUGA/ECHO 	X		X	X	
Symptom Assessment/ Adverse Events		X	X	X	
Dispense Study Vaccine		X	X		
60 minutes post vaccine vitals 		X	X		
Medical Record Chart review					X 

Must occur within 3 weeks (21 days) of 1st vaccination with the exception of CMP, CBC, HbA1c and ECHO/MUGA which must be in acceptable range within 90 days of enrollment

Physical Exam includes: Weight, vital signs, symptom/toxicity assessment, and ECOG scoring

Performed on females who are having sex that could lead to pregnancy.

Complete blood count (CBC) includes differential and platelets.

Complete blood count (CBC) with differential and platelets does not need to be drawn if completed within 90 days of enrollment.

Comprehensive Metabolic Panel (CMP) includes serum electrolytes, creatinine, BUN, AST, ALT, alkaline phosphatase, and total bilirubin. For vaccine visits follow glucose monitoring per section 8.5.1.1.

During the consent process, and at subsequent visits, patients will be instructed to hydrate sufficiently prior to visits requiring large volume blood draws.

Tetanus-diphtheria immunization only given if patient has not received one within 6 months.

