MUGA or ECHO to determine LVEF will be performed at baseline (if not completed within 90 days of prior to enrollment), prior to 2nd vaccination and 1 month post study treatment. Once a patient has had the baseline LVEF results, the same monitoring modality should be used for all subsequent LVEF evaluations. The MUGA/ECHO prior to 2nd vaccination and at 1 month post can be performed within 1 week of their scheduled visit.

Vaccines are scheduled 28 (+7) days from the previous vaccine.

The 1-month post vaccine visit should occur 28 (+7) days following the last vaccine. The 6-month post vaccine visit should occur 168 ( $\pm$  14) days following the last vaccine.

Follow-up includes requesting MD notes, clinical labs and imaging reports.

 60 minutes Post vaccine vitals may be collected 55-75 minutes after vaccination.

 Long-term follow up data, beyond the 6 month follow-up visit, will be kept and managed by the IND Sponsor (University of Washington).

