#### 8.5.1. Criteria for Premature Study Termination

Benchmarks for the safety of a dose level will be that there are no attributable (definitely, probably and possibly-related to study drug) grade 4 toxicity and <30% incidence of attributable Grade 3 toxicity (definitely, probably and possibly related to the study agent except as noted in the table below). If the observed rate of each of these toxicities is consistent with these benchmarks, escalation to the next higher dose level will be allowed.

Escalation will not be allowed if the observed toxicity rate exceeds the above. Other participants at the same dose level without toxicities will be allowed to continue at that dose level.

For grade 1 or 2 vaccine-related reactions, patients may be treated with acetaminophen or diphenhydramine as clinically indicated at the discretion of the study clinician and continue to receive vaccinations. For this prevention study  $\geq$  grade 3 attributable toxicity (other than those listed below; CTEP CTCAE v4.0) is considered dose-limiting for the patient. If grade 3 toxicity that is at least possibly related to the vaccine (except as described below) is observed, no further immunizations will be administered to that patient.

If  $\geq 3$  participants experience a grade 3 attributable toxicity, except as noted in the table below, or if any participant experiences a grade 4 attributable toxicity within any dose level, further accrual at that dose level will stop and accrual to the study will be terminated.

Category	Grade 3 Attributable Toxicity/AE	Allowable Duration
General disorders and administration	Flu-like symptoms	1 week
Musculoskeletal and connective tissue disorders	Arthralgia	1 week
	Myalgia	1 week
Investigations	Lymphocyte count decreased	2 weeks
	Platelet count decreased	1 week
	Hemoglobin decrease	1 week
	White blood cells decreased	2 weeks

We would consider a grade 3 or 4 autoimmune event a dose limiting toxicity and would consider steroid administration for grade 3 or 4 adverse immune related events that have been reported with other immune based therapies, i.e. ipilimumab. Examples of such immune related AEs include; rash, diarrhea/colitis, and hepatitis. The following dose schedule may be used:

Day 1-2: Intravenous Solu-Medrol at 1 mg/kg  
Day 3-4: Prednisone at 30 mg BID PO q day  
Day 4-5: Prednisone at 15 mg BID PO q day  
Day 5-6: Prednisone at 10 mg BID PO q day  
Day 6-7: Prednisone at 10 mg PO q day  
Day 8-9: Prednisone at 5 mg PO q day

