### **13.3 Accrual and Feasibility**

The study will accrue 30 evaluable patients with up to 12 patients in each dose arm. We anticipate up to 15% of enrolled patients may fail to receive all three vaccinations and the 1 month post vaccine follow-up.

For information regarding the study population (including gender and minority considerations) please see Section 4.3 Inclusion of Women and Minorities.

In order to meet the primary objective of this study, AE information is collected at each of the study visits and reviewed by the study team on a regular basis. If patients are unable to complete to the one month post vaccination follow-up visit, AE information may be collected by phone if possible. For secondary objectives, the research samples will be batched after each cohort to achieve consistency in the assays.

When we batch the research samples we will run the baseline time point and post vaccine time point(s) for a patient (usually 4-5 patients at one time). With this we are looking at results of an individual (comparing their IFN-g response to their baseline) therefore the results can be analyzed together.

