### **13.4 Primary Objective, Endpoint(s), Analysis Plan**

A primary endpoint of the study is safety through the 6 month follow-up visit. Safety of the three escalating dose of WOKVAC will be assessed by adverse events as per CTCAE v4.0.

The type and grade of toxicities noted during the immunization regimen will be summarized. The duration of toxicities will also be summarized using descriptive statistics such as mean and standard deviation. All adverse events noted by the investigator will be tabulated according to the affected body system. The frequency and severity of adverse events will be summarized with a proportion and a 95% confidence interval. Despite lack of randomization, the incidence and severity of toxicity will be compared between successive dose groups using nonparametric test with the understanding that due to small sample size per dose group such test will have limited sensitivity to detect any small to moderate differences. These tests will be performed without adjustment for multiplicity of testing.

Demographic and baseline characteristics obtained at enrollment will be summarized in tabular or graphical formats with descriptive statistics.

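### Vaccine reactions expected to last 1-2 days are first asked about 28-35 days after each dose, so the dates and worst grade that feed the primary safety summary are largely recalled.

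*Combined protocol and SAP*

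**What the plan says.** Expected reactions are short. Section 6.2 says that in earlier studies using the same adjuvant "patients sometimes complained of mild to moderate flu like symptoms (fever, chills, achiness, and fatigue) for 1-2 days after vaccination", and it gives the same 1-2 day course for redness and tenderness at the injection site. Section 2.2 says of the 66-patient HER2 plasmid study: "The most common AEs were reaction at the injection site, and flu-like syndrome".

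AEs are gathered at visits. Section 13.3 states that "AE information is collected at each of the study visits and reviewed by the study team on a regular basis". In the 7.1 table, the row "Symptom Assessment/ Adverse Events" is marked only at the vaccination and post-vaccination visits. A footnote to that table reads "Vaccines are scheduled 28 (+7) days from the previous vaccine", and the 1-month follow-up visit has the same window after the third dose. On the day of a dose, 7.3.4 and 7.4.5 provide a 60-minute observation with vital signs. Section 13.3 allows telephone collection only for a patient who cannot complete the 1-month visit.

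The analysis needs more than a count. Section 11.1.2 requires onset date, end date and severity grade for every AE. Section 13.4 summarises type, grade and frequency, compares incidence and severity between successive doses, and adds: "The duration of toxicities will also be summarized using descriptive statistics such as mean and standard deviation". Section 8.5.1 has a table headed "Grade 3 Attributable Toxicity/AE", in which three symptoms (flu-like symptoms, arthralgia, myalgia) carry a one-week allowable duration.

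**The concern.** The reactions this vaccine is most expected to cause begin and end well inside the gap between two visits. A patient asked four to five weeks later may forget a brief episode, merge two of them, misplace its dates or misjudge its worst day.

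Grade is exposed as well as duration. Under the severity table in 11.1.3, the step from grade 1 to grade 2 turns partly on whether instrumental daily activities were limited, and that detail fades. The 13.4 summaries of frequency, grade and duration would then be least reliable for the commonest events in a first-in-human trial. Where a grade 3 symptom occurs, its recalled end date could also decide whether it falls within the 8.5.1 allowance.

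**Working it through.** The plan gives no figure for completeness of AE capture, so there is none to reproduce. Its only power figure (13.5) concerns the immunogenicity regression and has no bearing here.

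**Recall interval** (day of vaccination = day 0)
- Reaction ends on day 1 to 2 (6.2).
- Next visit falls on day 28 to 35 (7.1 footnotes on vaccine timing and on the 1-month visit; 7.4.5; 7.5).
- Shortest gap: 28 - 2 = 26 days. Longest gap: 35 - 1 = 34 days.
- The gap is the same after all three doses.

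**Can any other scheduled contact close the gap?**
- The 60-minute observation sees immediate reactions, not the peak or end of a 1-2 day one.
- The one-week stagger between the first and second patient of an arm (section 3) has no assessment attached in 7.1.
- The toxicity check of the first three patients takes place before vaccine 2, about a month after dose 1.

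**Illustration of under-recording** (both inputs are assumptions)

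Let p be the chance that a dose causes the reaction and q the chance that it is recalled at the next visit, independent between doses. Over three doses:
- true share of patients affected: 1 - (1 - p)^3
- recorded share: 1 - (1 - pq)^3

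| p | True share | Recorded, q = 0.6 | Recorded, q = 0.8 |
|---|---|---|---|
| 0.30 | 1 - 0.70^3 = 65.7% | 1 - 0.82^3 = 44.9% | 1 - 0.76^3 = 56.1% |
| 0.10 | 1 - 0.90^3 = 27.1% | 1 - 0.94^3 = 16.9% | 1 - 0.92^3 = 22.1% |

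The shortfall is about 10 to 21 points at p = 0.30 and 5 to 10 points at p = 0.10.

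For orientation on p, section 2.2 reports 208 AEs over 86 administrations in the IGFBP-2 study, 12% of them injection-site reactions: 0.12 x 208 / 86 = 0.29 recorded events per administration. That is another vaccine and a recorded rate, so p = 0.30 remains an assumption. The documents give nothing on q. The table covers only whether a reaction is recorded at all; it does not measure error in grade or duration.

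**The case against.** **A compromised stopping rule.** A reader might infer that the 8.5.1 count rests on memory. The documents do not support that.
- The 1-2 day flu-like reactions are described as mild to moderate, whereas the exemptions concern grade 3 events.
- Four of the seven exempt items (platelets, hemoglobin, lymphocytes, white cells) are laboratory values and do not depend on recall.
- A grade 3 symptom is harder to forget. Hospitalisation is reported as serious within 24 hours of knowledge (11.2), and clinically significant grade 3-4 events are followed to resolution or stability (11.1.5).
- For a 1-2 day event, the remembered duration would have to be wrong by about five days or more to cross one week.
- A large effect can be produced by assumption. With 10 patients and a true non-exempt grade 3 rate of 30%, the binomial chance of at least 3 events is 0.617; it falls to 0.398 if only 75% are recorded as grade 3. Nothing in the documents supports 75% or any other value.

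What remains is the occasional grade 3 symptom whose end date is uncertain.

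**A measured bias, or every vaccination affected.** Neither follows. The shortfall above is assumed, and only doses followed by a brief symptomatic reaction are touched.

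**Other sources of information.** Patients may volunteer reports. The medication log (5.5) may hold start and stop dates with indications. The Visit Guides and worksheets (12.3) and the separate data management and safety monitoring plans (12.1, 12.4) are not available here and could contain a diary. So the supportable statement is that the protocol states none, not that none exists.

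**Differential recall between open-label arms.** This is plausible but speculative. A form completed by unblinded patients would not remove it.

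None of this changes the visit intervals or the need for dates and grade in 11.1.2 and 13.4.

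**Conclusion.** The point holds for brief symptomatic reactions. As the protocol is written, the onset date, end date and worst grade of the commonest expected reactions are largely recalled about 26 to 34 days after they ended, and they enter the primary safety summary in that form. The interval follows directly from the documents and needs no assumption beyond the 1-2 day course given in 6.2.

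The size of the resulting under-recording is unknown. The 66% against 45-56% comparison rests on assumed reaction and recall rates with independence between doses, and should not be quoted as an estimate. The consequence for 8.5.1 is secondary, limited to three grade 3 symptoms, and cannot be quantified from the documents. Capture of serious and laboratory toxicity is not at issue in this point. This is a low-cost improvement to the primary endpoint data, not a defect that makes the trial uninterpretable.

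**What to change.** 1. In 7.1, 7.3 and 7.4, add a one-page memory aid started on the day of each vaccine and continued through day 7 or until any symptom still present has resolved, whichever is later. A form that stopped at day 7 could not settle a one-week duration. Items: site reaction, temperature, fatigue, myalgia, arthralgia, headache; start and stop dates; effect on daily activities. Staff review it with the patient at the next scheduled visit.
2. In 13.4, state that onset, end date and worst grade of these symptoms are taken from the staff-reviewed form.
3. Use the same dates when applying the existing symptom durations in 8.5.1. No threshold or management rule changes.
4. If the Visit Guides already contain such a form, cite it in these sections instead.

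Cost: one form per vaccination, a small burden on patients and a few minutes at visits already scheduled. Recorded event rates may rise, mainly at grade 1-2. Some additional grade 3 events that count in 8.5.1 are possible, and the study team should expect this when comparing rates with earlier studies.
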